### 3. Outcomes/Endpoints

#### Primary:

- Home-time: Total number of days spent alive and outside of a hospital, skilled nursing facility, or inpatient rehabilitation facility since discharge

#### Secondary:

- All-cause mortality: Ascertained on the basis of the death date recorded in the denominator/vital status file.
- All-cause readmission: Readmission date will be ascertained from the inpatient institutional file.
- Stroke/TIA readmission: Readmission date will be ascertained from the inpatient institutional file and determined by ICD-9-CM principal diagnoses code of 430, 431, 432.x-435.x, and 436 on the inpatient claim. Ischemic stroke and hemorrhagic stroke will be analyzed separately.
- Cardiovascular readmission: CV Readmission date will be ascertained from the inpatient institutional file and determined by DRG 104–112, 115–118, 121–145, 479, 514–518, 525–527, 535, 536, and 547–558 on the inpatient claim.
- Non-cardiovascular readmission: All readmissions not meeting CV readmission criteria.
- Depression related readmission: Completed suicide, suicide attempt or major depressive episode (major depressive disorder [296.2, 296.3, 296.5, 298.0, or 311], completed suicide/suicide attempt [E950-E959\*], suicide ideation [V62.84], or suicide tendencies [300.9])

\*Given the potential for under-capture of completed suicides and suicide attempts, depression-related admission outcomes will be considered exploratory (reference: [http://www.minsentinel.org/work\\_products/HealthOutcomes/MS\\_HOI\\_SuicideReport.pdf](http://www.minsentinel.org/work_products/HealthOutcomes/MS_HOI_SuicideReport.pdf))

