## 2. Other variables

Demographics: Age, race, gender, insurance status, medical history (depression, stroke, TIA, DM, CAD, AF, HF, HTN, PVD, smoking)

Presentation variables: EMS transport, ambulatory status, initial NIHSS, prior antidepressant use

In-hospital variables: Dysphagia screening, DVT prophylaxis, t-PA, t-PA date/time, VTE interventions, documented DVT/PE, antithrombotics by day 2

Discharge variables: Discharge disposition, ambulatory status at discharge, ICD-9 discharge diagnosis, Antiplatelet/anticoagulant/HTN/AD meds, stroke education, smoking cessation, assessment for rehabilitation services

Hospital variables: Primary stroke center; comprehensive stroke center, teaching status, hospital bed size, rural location, region, annual volume of IS admissions

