## III. Analysis Tasks

### 1. Objective 1

**Aim:** To describe patient and hospital characteristics in the study population by discharge AD.

**Analysis:** Patient characteristics including demographics, medical history, initial vital signs, lab results and hospital characteristics will be described for the study population by discharge AD use. Categorical variables will be presented as proportions, and continuous variables will be presented as mean (standard deviation). We will compare the respective distributions of baseline characteristics among patients receiving 1) Any AD vs. no AD, and 2) SSRI vs. non-SSRI. Differences between groups will be evaluated using chi-square tests for categorical variables and Kruskal-Wallis tests for continuous variables.

**Output:** [Table 1](#) (patient baseline table)

**Table 1A.** Baseline characteristics of GWTG-Stroke-CMS patients by discharge AD use.

Variables	AD at Discharge	No AD at Discharge	Standardized differences, %	P-value*
------------------	------------------------	---------------------------	------------------------------------	-----------------

**Table 1B.** Baseline characteristics of GWTG-Stroke-CMS patients by discharge AD type.

Variables	SSRI at Discharge	Other AD at Discharge	Standardized differences, %	P-value*
------------------	--------------------------	------------------------------	------------------------------------	-----------------

(Detailed table entries on next page)

**Table 1.** Baseline characteristics of GWTG-Stroke-CMS patients\* overall and by discharge AD.

Variables	AD at Discharge	No AD at Discharge	StdDiff, %	P-value*
Demographics				
Age, year, mean (SD)				
Gender: Female				
Race/Ethnicity				
Medical History				
Depression				
Atrial Fibrillation				
Stroke/TIA				
CAD/MI				
Carotid Stenosis				
Diabetes Mellitus				
PVD				
Hypertension				
Smoker				
Dyslipidemia				
Heart Failure				
Medications prior to admission				
Antidepressants				
Anti-hypertensives				
Cholesterol-reducers				
Diabetic medications				
Presentation				
EMS transport				
Initial NIHSS				
Onset to arrival times (Prehospital delay)				
<2 hours				
2-4 hours				
>4 hours				
Symptoms resolved at time of presentation				
Ambulatory status on admission				
Labs				
Body Mass Index, mean (SD)				
Systolic blood pressure, mean (SD)				
Hemoglobin A1C, mean (SD)				
LDL-C, mean (SD)				

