Hospital characteristics				
Teaching status				
Rural location				
Region				
Primary Stroke Centers				
Comprehensive Stroke Centers				
Hospital size, mean (SD)				
Annual IS admission volume, mean (SD)				

All numbers presented are proportions of patient in the study population, unless specified otherwise.

\* P-values from chi-squared tests for independence for categorical variables and Wilcoxon rank sum tests for continuous variables

## 2. Objective 2

**Aim:** To estimate the associations between antidepressant use (any vs. none) and outcomes (home time, all-cause mortality, all-cause readmission recurrent stroke [ischemic, hemorrhagic], cardiovascular rehospitalization, and depression-related hospitalization [suicidality or major depressive episode] following discharge).

**Analysis:** Because patients who receive AD may differ from those who do not on important baseline and clinical characteristics that may affect the likelihood of adverse events, we will use inverse probability of treatment weighting (IPW) when assessing treatment effects. IPT weighting will be accomplished in two steps: First, we will use a logistic regression model to assign a probability of treatment selection to each patient based on the distribution of a defined set of covariates (listed above). The binary outcome for the selection model will be AD treatment (Y/N). In the second step, we will weight subject by the inverse of this assigned treatment probability, resulting in a pseudo-randomization of patients to AD vs. no AD treatment. The distribution of baseline patient characteristics for each treatment group will be assessed after weighting to determine adequacy of the selection model.

Following IPW, we will compare primary and secondary endpoints between treatment groups. Unadjusted rates of all-cause mortality, all-cause readmission, CV readmission, depression-related admission and stroke/TIA readmission will be examined using a Cox proportional hazards model with AD use as the single independent variable. Adjusted event rates will then be estimated using the same model with IPW included for each subject. Within-hospital clustering will be accounted for using robust estimator approach.

Home time will be examined first as a continuous variable in a linear regression model and then as a dichotomous outcome in an IPW-weighted logistic regression model, using 100% of time spent at home over 1 year as the primary outcome of interest.

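### The Stroke/TIA readmission code range takes 433.x and 434.x whole, so arterial occlusion or stenosis without infarction counts as an event, and the ischemic and hemorrhagic rows have no code lists of their own

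*SAP*

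**What the plan says.** Under 3. Outcomes/Endpoints, Secondary, the SAP defines one combined outcome, Stroke/TIA readmission, from the inpatient file by principal ICD-9-CM diagnosis, and its next sentence announces separate analyses: "430, 431, 432.x-435.x, and 436 on the inpatient claim. Ischemic stroke and hemorrhagic stroke will be analyzed separately". The outcomes table under Objective 2 (Table 3) accordingly has a Stroke/TIA row and separate rows for ischemic and hemorrhagic stroke. No section assigns codes to those two rows.

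The aim of Objective 2 names the construct more narrowly, in the run "all-cause readmission recurrent stroke [ischemic, hemorrhagic], cardiovascular rehospitalization". The combined outcome goes into a Cox model, first unadjusted ("stroke/TIA readmission will be examined using a Cox proportional hazards model with AD use as the single independent variable") and then with inverse probability weights.

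Neither document separates planned from unplanned readmissions. The all-cause definition, for example, reads in full: "All-cause readmission: Readmission date will be ascertained from the inpatient institutional file".

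The baseline table has a row for "Carotid Stenosis". The list under 2. Other variables does not include it: "medical history (depression, stroke, TIA, DM, CAD, AF, HF, HTN, PVD, smoking". The propensity model refers back to covariates listed earlier without saying which list is meant.

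**The concern.** A readmission outcome built from claims is only as specific as its code list. The SAP names ICD-9-CM, and in that code set the fifth digit of 433 (precerebral arteries) and 434 (cerebral arteries) separates disease without mention of infarction (0) from disease with infarction (1). TIA has its own category, 435. A wildcard on 433 and 434 therefore admits claims that report a narrowed or blocked artery and no new cerebral event.

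The study population has just been discharged after an ischemic stroke, is aged 65 or over, and is followed to 1 year. Some of these patients may return for treatment of the artery behind the index stroke. If such an admission carries a 433.x0 or 434.x0 principal diagnosis, it is reported as Stroke/TIA readmission although it is a consequence of the index event.

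Two things are at stake. Non-stroke events pull the hazard ratio away from the value for true stroke and TIA. And if carotid disease, or referral for its treatment, differs between patients with and without a discharge antidepressant, part of the reported association concerns arterial disease rather than recurrent stroke.

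**Working it through.** **1. Is there a figure to reproduce?** No. Neither document states an event rate, event count, hazard ratio or power for stroke/TIA readmission. The point turns on reading the code range. The arithmetic below only illustrates it.

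**2. The range set against the construct.** Code meanings are those of ICD-9-CM, the set the SAP names. The documents do not spell them out.

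| Code | Meaning | In the written range? | Stroke or TIA? |
|---|---|---|---|
| 430, 431, 432.x | intracranial hemorrhage | yes | yes |
| 433.x1, 434.x1 | occlusion/stenosis with infarction | yes | yes |
| 433.x0, 434.x0 | occlusion/stenosis without mention of infarction | yes | no |
| 435.x | transient cerebral ischemia | yes | yes (TIA) |
| 436 | acute, ill-defined cerebrovascular disease | yes | treated as stroke |

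The third line is the discrepancy. Nothing elsewhere removes it: there is no fifth-digit rule and no exclusion of planned or procedural admissions.

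**3. The ischemic row.** Within the range, infarction codes occur only in 433 and 434, with 436 as the non-specific code. The only form in which 433 and 434 are written is with the wildcard. Carrying that form into the ischemic row is the natural reading, but the SAP does not state it.

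**4. Illustration: dilution.** Let f be the share of counted events in the no-antidepressant group that are 433.x0 or 434.x0. If f is constant over follow-up, the hazards of the two event types add, so

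observed HR = (1 − f) × HR(stroke) + f × HR(non-stroke).

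To get a range for f, assume 1-year ischemic stroke readmission of 6–10% and non-infarct admissions of 1–3%. Neither range is in the documents.

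- Lowest f: 1/(10 + 1) = 9%. Midpoint: 2/(8 + 2) = 20%. Highest: 3/(6 + 3) = 33%.
- With true HR 1.20 and non-stroke HR 1.0:
  - f = 9%: 0.91 × 1.20 + 0.09 × 1.0 = 1.18
  - f = 20%: 0.80 × 1.20 + 0.20 × 1.0 = 1.16
  - f = 33%: 0.67 × 1.20 + 0.33 × 1.0 = 1.13

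These shares use ischemic stroke alone as the true-event denominator. For the combined outcome, which also counts TIA and hemorrhage, the same inputs give a smaller f and less dilution.

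**5. Illustration: direction.** Take a true stroke HR of 0.80 and f = 20%.

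- Non-stroke HR 1.0: 0.80 × 0.80 + 0.20 × 1.0 = 0.84
- Non-stroke HR 0.7: 0.80 × 0.80 + 0.20 × 0.7 = 0.78
- Non-stroke HR 1.3: 0.80 × 0.80 + 0.20 × 1.3 = 0.90

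The observed value can fall on either side of 0.80.

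**6. Illustration: precision.** Events needed by the Schoenfeld formula, (1.96 + 1.28)² / [p(1 − p)(ln HR)²], at two-sided 5% and an assumed 90% power, with p = 7,593/29,177 = 0.260 from the SAP's exposure table: 1,097 at HR 0.80 and 1,796 at HR 0.84.

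**The case against.** Five objections deserve weight.

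**The range defines the combined outcome only.** A reader might infer that the SAP counts carotid admissions as ischemic stroke. It does not say so. The ischemic row has no code list, and the programmer may intend a narrower one. This objection stands in full. What remains is that the combined outcome is affected as written and that the sub-outcomes are undefined.

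**Frequency is unknown.** A reader might also infer that planned carotid admissions are common after stroke and visibly inflate the event rate. The documents say nothing about how often such admissions occur or how they are coded. The carotid stenosis row records medical history at baseline, not later procedures. This stands too, so the shares used above are assumptions and not estimates.

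**The outcome is secondary.** Home-time does not use these codes. Nor do mortality, all-cause readmission, the DRG-based cardiovascular outcome or the depression-related outcome. Correct, and it limits the priority.

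**Weighting deals with group differences.** The planned weights draw on variables related to fitness for a procedure, such as NIHSS, ambulatory status, coronary disease, heart failure and peripheral vascular disease, and balance is checked after weighting. This stands in part. Weighting addresses confounding, not what the outcome counts, so dilution persists under perfect balance. It is also unclear whether carotid stenosis, the covariate closest to the problem, is in the model.

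**Broad code lists protect sensitivity.** Some true strokes are miscoded with fifth digit 0, and a narrow list loses them. That is a fair reason to keep the broad range as a sensitivity analysis, but not to use it as the main definition of an outcome named recurrent stroke.

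**Conclusion.** The point holds for the combined Stroke/TIA readmission outcome. The written range counts 433.x0 and 434.x0, which are neither stroke nor TIA under the SAP's own code set, and no rule removes planned admissions that carry them. For the ischemic row the finding is conditional: it is affected if the wildcards are carried over, and at present it has no definition at all.

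Size and direction cannot be derived from the documents. Under the assumed 9–33% non-stroke share with a null effect on those events, a true hazard ratio of 1.20 would be seen as about 1.18 to 1.13, a modest dilution. If those admissions are related to antidepressant use, bias in either direction is possible; the documents give no evidence that they are. The conclusion rests on the ICD-9-CM meaning of the fifth digit and not on any assumed rate. The change should be made, but it concerns a secondary outcome and does not touch the primary analysis.

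**What to change.** Replace the single range with explicit principal-diagnosis lists:

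- Ischemic stroke: 433.x1, 434.x1 or 436.
- TIA: 435.x.
- Hemorrhagic stroke: 430, 431 or 432.x.
- Stroke/TIA readmission: the union of the three.

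Report 433.x0 and 434.x0 by exposure group as a separate occlusion/stenosis row, so that their number is visible and planned carotid admissions with these codes no longer enter the stroke rows. Keep the present broad range as a named sensitivity analysis to cover strokes miscoded with fifth digit 0. Add carotid stenosis to the propensity covariates, and state which list the model uses.

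The cost is one code-list edit, one table row, one repeated model and one covariate that the SAP already plans to tabulate. No new data are needed. The downside is the loss of some miscoded true strokes from the main definition, which the sensitivity analysis will show.

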## III. Analysis Tasks

### 1. Objective 1

**Aim:** To describe patient and hospital characteristics in the study population by discharge AD.

**Analysis:** Patient characteristics including demographics, medical history, initial vital signs, lab results and hospital characteristics will be described for the study population by discharge AD use. Categorical variables will be presented as proportions, and continuous variables will be presented as mean (standard deviation). We will compare the respective distributions of baseline characteristics among patients receiving 1) Any AD vs. no AD, and 2) SSRI vs. non-SSRI. Differences between groups will be evaluated using chi-square tests for categorical variables and Kruskal-Wallis tests for continuous variables.

**Output:** [Table 1](#) (patient baseline table)

**Table 1A.** Baseline characteristics of GWTG-Stroke-CMS patients by discharge AD use.

Variables	AD at Discharge	No AD at Discharge	Standardized differences, %	P-value*
------------------	------------------------	---------------------------	------------------------------------	-----------------

**Table 1B.** Baseline characteristics of GWTG-Stroke-CMS patients by discharge AD type.

Variables	SSRI at Discharge	Other AD at Discharge	Standardized differences, %	P-value*
------------------	--------------------------	------------------------------	------------------------------------	-----------------

(Detailed table entries on next page)

**Table 1.** Baseline characteristics of GWTG-Stroke-CMS patients\* overall and by discharge AD.

Variables	AD at Discharge	No AD at Discharge	StdDiff, %	P-value*
Demographics				
Age, year, mean (SD)				
Gender: Female				
Race/Ethnicity				
Medical History				
Depression				
Atrial Fibrillation				
Stroke/TIA				
CAD/MI				
Carotid Stenosis				
Diabetes Mellitus				
PVD				
Hypertension				
Smoker				
Dyslipidemia				
Heart Failure				
Medications prior to admission				
Antidepressants				
Anti-hypertensives				
Cholesterol-reducers				
Diabetic medications				
Presentation				
EMS transport				
Initial NIHSS				
Onset to arrival times (Prehospital delay)				
<2 hours				
2-4 hours				
>4 hours				
Symptoms resolved at time of presentation				
Ambulatory status on admission				
Labs				
Body Mass Index, mean (SD)				
Systolic blood pressure, mean (SD)				
Hemoglobin A1C, mean (SD)				
LDL-C, mean (SD)				
Hospital characteristics				
Teaching status				
Rural location				
Region				
Primary Stroke Centers				
Comprehensive Stroke Centers				
Hospital size, mean (SD)				
Annual IS admission volume, mean (SD)				

All numbers presented are proportions of patient in the study population, unless specified otherwise.

\* P-values from chi-squared tests for independence for categorical variables and Wilcoxon rank sum tests for continuous variables

## 2. Objective 2

**Aim:** To estimate the associations between antidepressant use (any vs. none) and outcomes (home time, all-cause mortality, all-cause readmission recurrent stroke [ischemic, hemorrhagic], cardiovascular rehospitalization, and depression-related hospitalization [suicidality or major depressive episode] following discharge).

**Analysis:** Because patients who receive AD may differ from those who do not on important baseline and clinical characteristics that may affect the likelihood of adverse events, we will use inverse probability of treatment weighting (IPW) when assessing treatment effects. IPT weighting will be accomplished in two steps: First, we will use a logistic regression model to assign a probability of treatment selection to each patient based on the distribution of a defined set of covariates (listed above). The binary outcome for the selection model will be AD treatment (Y/N). In the second step, we will weight subject by the inverse of this assigned treatment probability, resulting in a pseudo-randomization of patients to AD vs. no AD treatment. The distribution of baseline patient characteristics for each treatment group will be assessed after weighting to determine adequacy of the selection model.

Following IPW, we will compare primary and secondary endpoints between treatment groups. Unadjusted rates of all-cause mortality, all-cause readmission, CV readmission, depression-related admission and stroke/TIA readmission will be examined using a Cox proportional hazards model with AD use as the single independent variable. Adjusted event rates will then be estimated using the same model with IPW included for each subject. Within-hospital clustering will be accounted for using robust estimator approach.

Home time will be examined first as a continuous variable in a linear regression model and then as a dichotomous outcome in an IPW-weighted logistic regression model, using 100% of time spent at home over 1 year as the primary outcome of interest.

Methods will be repeated for SSRI vs. non-SSRI with corresponding modeling of clinical outcomes.

**Output:** [Table 2](#) (AD vs No AD), [Table 3](#) (SSRI vs not SSRI)

**Table 2.** AD use and clinical outcomes following ischemic stroke discharge.

Outcomes	AD	No AD (ref)	Unadjusted HR (95% CI)	Adjusted HR (95% CI)	P-value
----------	----	----------------	---------------------------	-------------------------	---------

**Table 3.** SSRI vs. non-SSRI use and clinical outcomes following ischemic stroke discharge.

Outcomes	SSRI	Other AD (ref)	Unadjusted HR (95% CI)	Adjusted HR (95% CI)	P-value
Home time: 100% (OR)					
All-cause mortality					
Readmission					
All-cause					
Cardiovascular					
Stroke/TIA					
Ischemic Stroke					
Hemorrhagic Stroke					
Depression-related readmission					
			Unadjusted Difference (95% CI)	Adjusted Difference (95% CI)	
Home time days, mean (SD)					

[figure not shown]
### 3. Objective 3

**Aim:** To describe 1y mortality and readmission outcomes by plotting the cumulative incidence functions.

**Analysis:** We will limit the population to patients naïve to AD on admission and construct Kaplan-Meier curves for all-cause mortality at 1 year following the index hospitalization for patients prescribed AD at hospital discharge. Log-rank tests will be used to examine mortality differences between AD treatment groups.

For the other non-mortality endpoints, we will calculate incidence at 1 year based on estimates from the cumulative incidence function, to account for the competing risk of mortality. Gray tests will be used to test for differences between groups for these outcomes.

We will then restrict the study population to patients receiving AD at hospital discharge and analyses will be repeated for SSRI vs. non-SSRI antidepressants.

**Figure X.** Cumulative incidence plots for mortality and readmissions by AD types (Yes vs No, and again for SSRI vs Non-SSRI).

### 4. Objective 4

**Aim:** Perform subgroup analyses.

**Analysis:** Because AD use and outcomes may vary by patient characteristics, we will repeat modeling of these associations by the following subgroups: Age (65-80, 80-90, 90+), sex (male vs. female), race (white vs. non-white), NIH stroke scale (<16 vs. ≥16), and medical history of depression.

Repeat Tables 2 and 3 in subgroups defined.

### 5. Objective 5

**Aim:** To describe baseline patient and hospital characteristics in the prospectively enrolled PROSPER study population with ischemic stroke discharge by discharge antidepressant use (any vs none).

**Analysis:** Patient characteristics including demographics, medical history, initial vital signs, lab results and hospital characteristics will be described for the study population by discharge AD use (any vs

none). Categorical variables will be presented as proportions, and continuous variables will be presented as mean (standard deviation). We will compare the respective distributions of baseline characteristics among patients receiving any AD vs. none. Differences between groups will be evaluated using chi-square tests for categorical variables and Kruskal-Wallis tests for continuous variables.

**Output:** Table 5A. (patient baseline table)

**Table 5A.** Baseline characteristics of prospectively enrolled PROSPER patients with ischemic stroke discharge by discharge AD use.

Variables	AD at Discharge	No AD at Discharge	StdDiff, %	P-value*
Demographics				
Age, year, mean (SD)				
Gender: Female				
Race/Ethnicity				
Medical History				
Depression				
Atrial Fibrillation				
Stroke/TIA				
CAD/MI				
Carotid Stenosis				
Diabetes Mellitus				
PVD				
Hypertension				
Smoker				
Dyslipidemia				
Heart Failure				
Medications prior to admission				
Antidepressants				
Anti-hypertensives				
Cholesterol-reducers				
Diabetic medications				
Presentation				
EMS transport				
Initial NIHSS				
Onset to arrival times (Prehospital delay)				
<2 hours				
2-4 hours				
>4 hours				
Symptoms resolved at time of presentation				
Ambulatory status on admission				
Labs				
Body Mass Index, mean (SD)				
Systolic blood pressure, mean (SD)				
Hemoglobin A1C, mean (SD)				
LDL-C, mean (SD)				
Hospital characteristics				
Teaching status				
Rural location				
Region				
Primary Stroke Centers				
Comprehensive Stroke Centers				
Hospital size, mean (SD)				
Annual IS admission volume, mean (SD)				

All numbers presented are proportions of patient in the study population, unless specified otherwise.

\* P-values from chi-squared tests for independence for categorical variables and Wilcoxon rank sum tests for continuous variables

[figure not shown]
**Table 5B.** Baseline characteristics of prospectively enrolled PROSPER patients with ischemic stroke discharge by discharge AD type.

Variables	SSRI at Discharge	Other AD at Discharge	StdDiff, %	P-value*
Demographics				
Age, year, mean (SD)				
Gender: Female				
Race/Ethnicity				
Medical History				
Depression				
Atrial Fibrillation				
Stroke/TIA				
CAD/MI				
Carotid Stenosis				
Diabetes Mellitus				
PVD				
Hypertension				
Smoker				
Dyslipidemia				
Heart Failure				
Medications prior to admission				
Antidepressants				
Anti-hypertensives				
Cholesterol-reducers				
Diabetic medications				
Presentation				
EMS transport				
Initial NIHSS				
Onset to arrival times (Prehospital delay)				
<2 hours				
2-4 hours				
>4 hours				
Symptoms resolved at time of presentation				
Ambulatory status on admission				
Labs				
Body Mass Index, mean (SD)				
Systolic blood pressure, mean (SD)				
Hemoglobin A1C, mean (SD)				
LDL-C, mean (SD)				
Hospital characteristics				
Teaching status				
Rural location				
Region				
Primary Stroke Centers				
Comprehensive Stroke Centers				
Hospital size, mean (SD)				
Annual IS admission volume, mean (SD)				

## 6. Objective 6

**Aim:** To estimate the associations between antidepressant use (any vs. none) and patient reported outcomes (modified Rankin Scale, EQ-5D-3L Health Profile, PHQ-2 score, SIS-16 score and Fatigue Severity Scale score).

**Figure 6.** Grotta bar showing AD vs no AD use and mRS following ischemic stroke discharge.

